9.7. PK Population

The PK population will consist of all ITT population participants with at least one post-dose PK result. Participants will be analysed according to the treatment they received.

10. PLANNED STATISTICAL METHODS

10.1. Statistical Considerations

10.1.1. General Definitions

In all applicable summary/analysis presentations of safety endpoints, Baseline is defined as the last non-missing assessment value for a participant, for that particular parameter, that is prior to inoculation of challenge virus, unless over-ruled after review of data at the BDRM or otherwise stated in the appropriate endpoint sections below, whatever the reason for that assessment (e.g. if it is a repeat assessment, then it should be used as the baseline). For efficacy endpoints, the baseline definition is as per the appropriate endpoint sections below. For the derivation of most efficacy endpoints, the first assessment to be used should be the assessment that was taken at the time of first administration of IMP. For example, if a participant was first dosed on the morning of Day 3 then the first qRT-PCR value to be used in the AUC of qRT-PCR viral load (from time of first administration) derivation should be the Day 3 morning assessment. For endpoints using symptom diary card data, the definition of baseline will be defined in greater detail within the appropriate sections of the SAP.

A participant will be classed as infected, and therefore randomised to be dosed, when they have a positive result for RSV-A Memphis 37b by qualitative integrative cycler polymerase chain reaction (qicPCR) from nasal wash sample. IMP administration will be initiated 12 hours after a positive result. However, if a participant remains uninfected, IMP administration will begin on the evening of Day 5.

For participants that extend their time in quarantine beyond Day 12, the additional assessments beyond Day 12 will be listed only, and will not be used for the derivation of any efficacy endpoints. For the avoidance of doubt, the assessment performed on the morning of Day 12 will be the final assessment used for all analyses and summaries for all participants. If additional assessments are taken on Day 12, then they will be listed only. However, the use of data beyond the morning of Day 12 will be discussed at the BDRM.

A participant will be considered to have completed the study after their attendance at the last planned study visit (Day 28 (\pm 3 days)), or the last unscheduled visit (if any occur), as applicable.

Data recorded for replaced participants will be listed. However, these participants will only be included in tables where they meets the inclusion criteria for the relevant population.

Within summary presentations/analyses it is envisaged that only scheduled protocol visit values will be used for post-baseline time points and unscheduled visits will not be summarised in tables. All unscheduled visits will be listed. However, at the BDRM the occurrence of such non-scheduled data will be reviewed for each participant to decide if (and how) any such data point(s) should be included within summary presentations/analyses. Any such decisions will be documented in the BDRM minutes.

For assessments made on Day 0 (either pre or post challenge), the date and time of inoculation will be compared to the date and time of assessment to ensure they are assigned to either pre or post challenge accurately.

10.1.2. Data Presentation

The specific format and content of each data presentation is shown in Section **Error! Reference source not found.**

Summary tables will be presented by treatment group. For demographic, baseline, and safety data these will also be summarised for all participants.

Within all Tables and Figures, the treatment groups will be labelled and ordered as follows:

- RV299
- Placebo
- Overall (including RV299 and placebo participants, for demographic, baseline and safety data)

The scheduled protocol visits will be labelled in report presentations as follows:

- “Admission (Day-2/Day-1)”
- “Day 0 (pre-HVC)”
- “Day 0 (HVC)”
- “Day 0 (post-HVC)”
- “Day x” (where x=1 to 12)
- “Follow-up (Day 28)”
- “Early Withdrawal”

As the study day of IMP administration day will differ between participants, “x Days from IMP Administration” (where x=0 to 11) will be presented for efficacy outputs relating to clinical symptoms and PK. These assessments should be presented in relation to the IMP administration, rather than the inoculation day.

For data with multiple assessments on one study day, each assessment will be numbered sequentially (e.g. Assessment 1, Assessment 2 etc.) and will be relative to the first administration of IMP. Further details will be provided in the relevant sections of the SAP.

Within some tables, only “Baseline” may be shown (as applicable) instead of the scheduled visits Day 0 (pre-HVC) and Day-2/Day-1 (with baseline being chosen as defined in Section 10.1.1 and in the relevant endpoint sections).

Where duplicate information is collected on both the database and on the vendor data transfer(s) (e.g., sampling date and time) this information will be reconciled by data management and then the information from the vendor data transfer(s) will be included in Participant Listings.

All variables will be listed to the same number of decimal places as reported. Continuous endpoints will be summarised by: n, n missing, mean, standard deviation (SD), %CV, median, lower quartile (Q1), upper quartile (Q3), minimum (Min) and maximum (Max). Where appropriate, 95% confidence intervals (CIs) for the mean and/or median may be presented. For selected summaries the geometric mean (GM) and geometric standard deviation (GSD) will also be presented to aid interpretation. The SD will only be presented in summaries where the corresponding n is greater than or equal to 3.

The number of decimal places (DP) each summary statistic is rounded to for display in the summary tables, relative to the number of DP the parameter is recorded to, is shown in Table 3.

Table 3: Number of decimal places to use to display each summary statistic.

Statistics	Number of DP for display
Min, Max	Same as recorded
Mean, GM, Median, Q1, Q3	1 more DP than recorded

SD, GSD, %CV, 95% CI 2 more DP than recorded

For endpoints that require a geometric mean to be produced, and those endpoints can have raw values of 0 (zero), the GM calculation will add an appropriate constant value to all raw values prior to logging and will subtract that constant value from the final calculated anti-logged mean. The constant value used will be documented in the footnote of the tables. The value is typically 1 however it may be another small value which is in line with the scale of the data should a value of 1 be unsuitable. The GM and GSD are calculated as follows:

$$GM = \text{anti-log} (\text{mean} (\log_{10} (\text{endpoint values} + \text{constant}))) - \text{constant}$$

$$GSD = \text{anti-log} (\text{SD} (\log_{10} (\text{endpoint values})))$$

The %CV will be calculated as $\%CV = 100 * (SD / \text{mean})$ using untransformed values.

Categorical variables will be summarised using proportions (counts and percentages). The specific approach to calculating percentages (relevant denominator) is detailed within each (relevant) Table template (Section **Error! Reference source not found.**).

All collected data will be included within participant listings.

10.1.3. Early Withdrawal Visit

If a participant withdraws prior to Day 28 they will complete an early withdrawal visit. The data collected at this visit will be summarised as the nearest scheduled visit, unless the nearest visit already has data, in which case it will be summarised as the next scheduled visit. The data collected at the early withdrawal visit will be listed as the early withdrawal visit.

For example, if a participant withdraws at the Day 8 visit the data collected at the early withdrawal visit will be included in the summaries of Day 8. If, however, the participant withdrew between Day 8 and Day 9, after attending as normal on Day 8, the data collected at their early withdrawal visit will be included in the Day 9 summaries.

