Oral dosing with RV299	
 1) RV299 has not previously been tested in human subjects infected with RSV and may not confer any antiviral protection against RSV in humans despite encouraging pre-clinical evidence. 2) Pre-clinical studies have identified myelosuppressive effects (including reduced reticulocytes, platelets and white cell counts and fractions) in dogs following 14 days' administration at doses well in excess of the intended human dose (50mg/kg/day). No such effects were seen at 15mg/kg/day and this dose was used to set the NOAEL for human administration of RV299. 3) RV299 has shown variable PK with some subjects experiencing higher exposures (doubling) for a given dose than other subjects, possibly due to differences in clearance. 	
 1) Subjects will be monitored for severe RSV-related disease throughout the study and managed accordingly with supportive measures and may be withdrawn from the study at the investigator's discretion at any time. 2) The 65mg dose has been administrated to healthy human volunteers twice daily for 5 days and there has been no evidence of myelosuppressive effects during dosing or during the 3-week follow-up period after the last dose. The same study confirmed that the 65mg dose produces PK exposures in humans that are 2- to 4-fold below the NOAEL, providing an adequate safety margin. Subjects in the viral challenge study will have safety bloods assessed throughout the dosing interval and during follow-up to continue to monitor for any myelosuppressive effects. 3) The dose has been selected to ensure that the NOAEL safety margin is not exceeded even in subjects who may experience doubling in RV299 exposure for a given dose.
Oral dosing with placebo	Given that the placebo is a pharmacologically inert material, there should be no risk.	Not applicable.

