7.5. Stopping Rules

The PI/investigator and the SME will perform safety reviews on available clinical and virology data as appropriate during the quarantine period.

Three clinical scenarios relating to the incidence of SAEs/suspected unexpected serious adverse reactions (SUSARs) during the study and the procedures that should be performed in each case are presented in [Table 7-1](#).

Table 7-1: Study Stopping Rules

Status	Criterion	Procedure
1	A report has been received of one (or more) SUSAR(s) in any, one (or more) participant(s).	If such a status occurs at any point during the study, then further administration of the IMP will not take place. The PI/investigator and the SME will review the data and decide on whether it is appropriate to recommence IMP dosing (approval of a substantial amendment from the Competent Authorities is required) or terminate the study.
2	No SUSAR(s) have been reported but an overall pattern of clinical changes or symptoms exists, attributed to the IMP, which may appear minor or moderate in terms of individual AEs or SAEs, but which collectively represent a concern for safety.	If such a status occurs at any point during the study, then further administration of IMP will not take place. The PI/investigator and the SME will review the data and decide on whether it is appropriate to recommence IMP dosing (approval of a substantial amendment from the Competent Authorities is required) or terminate the study.
3	Unexpected virus-related SAE(s) or unexpected virus-related AE(s) of clinical concern have been reported following viral challenge.	If such a status occurs at any point during the study, then the PI/investigator and the SME will review the data and decide based on expectedness* of the viral event. If the event is unexpected, further administration of the virus will not take place. The PI/investigator and the SME will review the data and decide on whether it is appropriate to recommence inoculation (approval of a substantial amendment from the Competent Authorities is required) or terminate the study.

* Expectedness will be assessed by referring to the challenge virus dossier.

A final follow-up visit will be performed on Day 28 (± 3 days). Follow-up of any event should continue until resolution, stabilisation, it is judged by the PI/investigator to be no longer clinically significant, the participant is lost to follow-up, or an alternative explanation has been provided.

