10.1.5. Handling of Dropouts or Missing Data

No imputation methods will be used to manage the occurrence of missing data. Only observed data at each scheduled visit will be reported.

For adverse events and concomitant medications the approach to handle missing data has been described in Sections 10.9.1 and 10.5 respectively. For any other data which has partial dates, these dates will be completed using a suitably conservative approach.

Any other mechanisms to adjust for missing data will be outlined within the relevant endpoints section.

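### SAP 10.1.3 sets no distance limit, so after discharge on Day 12 early-withdrawal data from Days 13 to 24 are summarised as Day 28, outside that visit's ±3 day window

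*SAP*

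**What the plan says.** SAP 10.1.3 applies to every withdrawal before the final visit: "If a participant withdraws prior to Day 28 they will complete an early withdrawal visit". In summaries the data go to the nearest scheduled visit, "unless the nearest visit already has data, in which case it will be summarised as the next scheduled visit". In listings they keep the early-withdrawal label. The section gives two examples, both inside quarantine. The second is the case where "the participant withdrew between Day 8 and Day 9, after attending as normal on Day 8"; those data are summarised as Day 9.

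SAP 10.1.2 sets out the visit grid ("The scheduled protocol visits will be labelled in report presentations as follows"). It runs daily from Day 1 to Day 12, then jumps to the Day 28 follow-up, and it also names Early Withdrawal as a visit label. Protocol 7.5 fixes the end of follow-up: "A final follow-up visit will be performed on Day 28", with a window of ±3 days. SAP 10.1.5 rules out imputation and adds: "Only observed data at each scheduled visit will be reported".

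**The concern.** The rule was evidently written for the daily visits of quarantine. Once a participant has been discharged, the next scheduled visit is 16 days after Day 12, and nothing in 10.1.3 stops data from early in that gap being carried to its far end. A value taken within a week of the last dose would then sit in the same column, and in the same change-from-baseline summary, as values taken about three weeks after it. Such values come only from people who left the study. The Day 28 count would also include participants who have no Day 28 observation.

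Day 28 is the only scheduled visit after discharge, and Protocol Table 2-1 says safety bloods will be assessed "during follow-up to continue to monitor for any myelosuppressive effects". A clean follow-up column is therefore worth having.

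**Working it through.** **Inputs**
- Visit grid: Days 1 to 12 daily, then Day 28 (SAP 10.1.2).
- Mapping rule: nearest visit; if filled, the next one (SAP 10.1.3).
- Day 28 window: ±3 days, so Days 25 to 31 (Protocol 7.5; SAP 6.1).
- First dose: between Day 2 evening and Day 5 evening (SAP 6.1).
- Course: 10 doses about 12 hours apart (SAP 6.1 and 10.6).

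**Step 1: the SAP's own examples.** Withdrawal at the Day 8 visit: nearest is Day 8, not yet filled, result Day 8. Withdrawal between Days 8 and 9 with Day 8 filled: in the first half of the interval the nearest visit is Day 8, which is filled, so the next is Day 9; in the second half the nearest is Day 9. Both give Day 9, as the SAP states. With daily visits the forward shift never exceeds 1 day.

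**Step 2: the same rule after discharge, with Day 12 attended.** The midpoint between the two visits is (12 + 28) / 2 = Day 20.

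| Early-withdrawal visit | Nearest visit | Summarised as | Days before Day 28 | Inside ±3 days? |
|---|---|---|---|---|
| Days 13 to 19 | Day 12 (filled) | Day 28 | 15 to 9 | No |
| Day 20 | Tie, 8 days to each | Day 28 either way | 8 | No |
| Days 21 to 24 | Day 28 | Day 28 | 7 to 4 | No |
| Days 25 to 27 | Day 28 | Day 28 | 3 to 1 | Yes |

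Days outside the window but assigned to Day 28: 24 − 13 + 1 = 12, of the 15 days from Day 13 to Day 27. For Days 13 to 20 the cause is the next-visit clause (or the tie); for Days 21 to 24 it is the nearest-visit clause alone. A cap on the next-visit clause only would therefore miss the last four days.

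**Step 3: time since last dose.** Tenth dose = first dose + 9 × 12 h = first dose + 4.5 days. That gives Day 7 morning at the earliest and Day 10 morning at the latest, assuming the full course is taken on schedule.
- Value taken on Day 13: 13 − 10 = 3 to 13 − 7 = 6 days after the last dose.
- Value taken on Day 28: 28 − 10 = 18 to 28 − 7 = 21 days after the last dose.

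**Step 4: how many.** The documents give no rate of withdrawal after discharge. Assuming 0 to 4 of the 80 planned participants, the share is 0 / 80 = 0% to 4 / 80 = 5%.

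**The case against.** The best defence is that very little depends on this. All safety analyses are descriptive (SAP 10.9). Efficacy stops at the morning of Day 12 (SAP 10.1.1). The affected path needs someone to withdraw after discharge and still attend a visit, which Protocol 7.1 asks for only where possible. Listings keep the early-withdrawal label, the laboratory listing shows collection date and study day, and the disposition table counts completers and withdrawals. All of that stands, and it keeps the point small. The blinded review's discretion over unscheduled visits (SAP 10.1.1) does not remove the point: that text does not mention early-withdrawal visits or override 10.1.3.

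Several stronger readings are tempting, and the documents do not support them:

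- *Late haematology would be distorted.* The Schedule of Events is not legible enough in the text available for this review to show which bloods are due at both Day 28 and early withdrawal. If haematology is not due at both, its Day 28 column is unaffected by scheduled withdrawal samples. The risk-table sentence refers to follow-up without naming Day 28.
- *Physical examinations are relabelled.* They are not. SAP 10.9.5 puts them in listings only.
- *Bloods taken during dosing are moved to a post-dosing time point.* That needs a scheduled visit to mean one at which that parameter is due. The SAP does not say so, and its example fits the plain reading, under which the shift in quarantine is at most a day.
- *10.1.3 contradicts 10.1.2 and 10.1.5.* The passages can be reconciled. The Early Withdrawal label in 10.1.2 has a use in listings, and the sentence in 10.1.5 follows a ban on imputation; assigning an observed value to a visit is not imputation.
- *Missing Day 28 data are hidden.* The by-visit count would overstate Day 28 attendance, but the listings and the disposition table would show the true position.

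**Conclusion.** The point holds as a small defect. Followed as written, SAP 10.1.3 tabulates as Day 28 any early-withdrawal data collected on Days 13 to 24 from a participant who attended Day 12. Those data are 4 to 15 days early against an allowed 3. At the extreme, a value from 3 to 6 days after the last dose is pooled with values from 18 to 21 days after it.

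The damage is limited to descriptive by-visit safety summaries, and within those to parameters collected at both visits; the sponsor should confirm which these are from its own schedule. The primary endpoint is not touched. The number affected is probably small, and 0 to 4 of 80 is an assumption, not a figure from the documents. No effect on any mean or change from baseline has been calculated, so nothing here shows that a safety conclusion would change.

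**What to change.** In SAP 10.1.3, keep the existing rule for withdrawals during quarantine; the Day 8 to Day 9 example is harmless and need not change. Add that, after the Day 12 assessment, early-withdrawal data are mapped to Day 28 only if they were collected within Day 28 ±3 days and no Day 28 record exists for that participant. Otherwise, summarise them under the Early Withdrawal label already listed in SAP 10.1.2 and count Day 28 as missing. The condition on an existing record also covers the withdrawn participant who is invited back for the final visit under Protocol 7.1, for whom the SAP at present does not say which record is used.

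The cost is a few sentences in the SAP and one extra row in the by-visit safety tables, which may hold very few values.

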10.1.4. Statistical Testing and Estimation

Statistical analyses for the primary and secondary endpoints will be performed using appropriate two-sided hypothesis tests at the 5% significance level.

For continuous data, an analysis of covariance (ANCOVA) will be used to compare means between the RV299 and placebo groups. The ANCOVA will have treatment group as a fixed effect and baseline viral load as a covariate, unless stated otherwise in the relevant endpoint section. Should data not satisfy the assumptions, an appropriate alternative test, e.g., Wilcoxon Rank-Sum test will be used.

P-values will be rounded to 4 decimal places. All p-values that round to 0.0000 will be presented as <0.0001 and p-values that round to 1.000 will be presented as >0.9999.

10.1.5. Handling of Dropouts or Missing Data

No imputation methods will be used to manage the occurrence of missing data. Only observed data at each scheduled visit will be reported.

For adverse events and concomitant medications the approach to handle missing data has been described in Sections 10.9.1 and 10.5 respectively. For any other data which has partial dates, these dates will be completed using a suitably conservative approach.

Any other mechanisms to adjust for missing data will be outlined within the relevant endpoints section.

10.1.6. Interim Analysis and Data Monitoring

No interim analyses are planned to be performed.

10.1.7. Multiple Comparison/Multiplicity

As this is an early phase study, no adjustments will be made to address multiplicity.

10.1.8. Model Checking and Sensitivity Analyses

Statistical hypothesis testing will be presented using parametric tests where an ANCOVA will be the preferred statistical method. However, if the parametric test assumptions fail, non-parametric alternatives will be presented.

The normality of the error term from fitted models will be checked by performing the Shapiro-Wilk's test of normality of the residuals and producing normality probability plots of the residuals.

For cases where the normality assumption fails to hold, the treatment effect will be assessed by the non-parametric Wilcoxon rank-sum test.

10.1.9. Data Conversion (CDISC)

For the reporting of this study there is no requirement for CDISC SDTM and/or ADaM standards to be applied.

10.1.10. Software

Data will be reported using SAS version 9.4 (SAS Institute Inc, Cary, North Carolina, USA).

10.2. Participant Disposition

The number of participants enrolled (signed ICF), the numbered receiving challenge agent inoculation, the number randomised, the number receiving at least one dose of IMP and receiving all doses of IMP, the number discontinuing IMP early, the number withdrawing from the study, those completing the study (Day 28 visit), and the numbers in each population will be summarised for all participants and by treatment group. The reasons for early discontinuation of IMP and reasons for withdrawal from the study will also be summarised by treatment group.

A listing will be provided including details of informed consent, randomisation and quarantine admission.

10.3. Protocol Deviations

Participants data will be reviewed for major protocol deviations by a qualified clinical reviewer prior to database lock and unblinding, at the BDRM. Participants with any major protocol deviations will be documented within the BDRM minutes, and such participants will be excluded from the PP population.

All protocol deviations will be listed.

